The purpose of the study is to determine if Clinpro™ 5000, Clinpro™ Tooth Crème, or MI-Paste Plus has an effect on the formation and resolution of white spot lesions for patients undergoing orthodontic treatment. This study will include 90 patients in the UAB Orthodontic Clinic.

14. Background—in nontechnical, lay language

Summarize in 2-3 paragraphs past experimental and/or clinical findings leading to the formulation of this study. Include any relevant past or current research by the Principal Investigator. For drug and device studies summarize the previous results (i.e., Phase I/II or III studies).

During the course of orthodontic treatment, the practitioner normally faces two common iatrogenic treatment side effects: root resorption and enamel decalcification, with the latter occurring at a much higher frequency. While the processes that lead to enamel demineralization are understood, methods to diminish or perhaps eliminate degradation of enamel surfaces are being searched for. Several approaches have been formulated to counteract demineralization of tooth structure. One approach involves patient compliance and consists of in-depth oral hygiene instructions, in-office fluoride applications, and at-home fluoride rinses, gels, and varnishes. An alternative approach, which possesses potential benefit regardless of patient compliance, includes the use of fluoride-releasing agents, such as composites, glass ionomers, sealants, and elastomeric ties.

Enamel decalcification or white spot formation, is a phenomenon occurring primarily on smooth enamel surfaces of teeth, notably within the gingival third of the crown. Demineralized enamel, the precursor to caries formation, can be attributed to fixed orthodontic appliances, and prolonged exposure to bacterial plaque. Bacterial plaque promotes the accumulation of acidic byproducts and demineralization that leads to successive changes in the optical properties of subsurface demineralized enamel. Progression to clinically detectable white spot lesions may occur as early as one month following the placement of orthodontic appliances.

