Over the past thirty years, numerous studies have reported an increase in white spot lesions following orthodontic treatment. While a large portion of the non-orthodontically-treated population experiences some form of decalcification, orthodontically treated patient populations have shown both an increase in new lesions and an increase in the severity of preexisting enamel opacities. Approximately, 50 percent of orthodontically treated patients develop white spot lesions in one or more teeth, compared with only 24 percent in those not undergoing orthodontic treatment.

Appliance removal halts white spot formation, and further elimination of cariogenic factors through diligent oral hygiene efforts inactivates incipient lesions, which may undergo regression over time. Complete elimination of lesions is unlikely due to the rapid remineralization of the enamel surface with high concentration fluorides, which restrict passage of ions into the deeper, more affected layers. Therefore, immediate application of high concentration of fluoride is not recommended. Decreased enamel discolorations may occur with time due to further remineralization, but regression is primarily credited to gradual surface abrasion of tooth structure.

Such problems with enamel decalcification in orthodontic patients have influenced clinicians to search for a solution to orthodontic-associated demineralization. Because fluoride treatment immediately upon debonding is not advocated, clinicians have proposed fluoride treatment and fluoride-releasing materials at the commencement of therapy. Recommended solutions include oral hygiene instruction and reinforcement, fluoridated toothpastes, varnishes and mouthwashes, and fluoridated water supply. Lack of patient compliance hinders these efforts.

Two new anti-cavity toothpastes, Clinpro™ 5000 with 1.1% Sodium Fluoride and Clinpro™ Tooth Crème with 0.21% Sodium Fluoride, are currently available and have been shown in some initial case reports to be useful in the reduction of white spot lesions. Clinpro™ restores minerals and helps you produce saliva. Both the Clinpro™ products are advanced formulas containing an innovative tri-calcium phosphate ingredient. They are available exclusively from 3M ESPE. Clinpro™ contains fluoride as well as calcium and phosphate, which are components naturally found in saliva.

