2. Patients that in the opinion of the investigator will be compliant with the use of the paste
3. Patients who have not used extensive fluoride regimes
4. 12 years and older
5. Subjects must use a non-fluoridated toothpaste (such as Tom's of Maine) for a one-week period prior to starting this trial.

EXCLUSION CRITERIA

1. Any medical or dental condition that in the opinion of the investigator could impact study results during the expected length of the study.
2. Patient is currently using any investigational drug.
3. Patient plans to relocate or move within six months of enrollment.
4. Patients who have or are currently undergoing fluoride treatment for white spot lesions.
5. Patients with IgE Casein Allergy

d. If participants will comprise more than one group or stratification, describe each group (e.g., treatment/intervention, placebo, controls, sham treatment) **and** provide the number of participants anticipated in each group.

Three groups of 30 subjects (one group with Clinpro™ 5000, one group with MI-Paste Plus, and one group with Clinpro™ Tooth Crème) each will be evaluated as a protocol for the reduction of white spot lesions at the start of orthodontic treatment. Subjects will be recruited through the Orthodontic Postgraduate Clinic at the University of Alabama at Birmingham School of Dentistry.

In order to fully evaluate each of the products, the selected product will be brushed on for two minutes twice daily for 4 months. After brushing on the product, patients should not rinse their mouths with water. Rather, they should just expectorate (spit) so they don't clear out the actives from the product. Patient should also not eat or drink for 30 minutes following the treatment.

Subjects will be reviewed every 4 weeks. Subjects and study administrator will not know if the investigational paste or placebo is being administered. However, the PIs will know. [name] and [name] will randomly choose subjects by drawing individual slips of paper from an envelope on which 30 of each study product (i.e., Clinpro™ 5000, MI-Paste Plus, or Clinpro™ Tooth Crème) will be written. Each subject will receive product based upon the treatment type written on the paper selected by PIs.

- e. Indicate which, if any, of the special populations listed below will be involved in the protocol. Include the Special Populations Review Form (SPRF) if indicated.
- Pregnant Women: Attach [SPRF—Pregnant Women, Fetuses, Neonates/Nonviable Neonates](#)

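### The Purpose asks whether the products work, but all 90 patients receive one of three study products, so the randomised comparison can estimate only differences between products

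*Protocol*

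**What the plan says.** **Question.** Protocol section 13 asks whether Clinpro 5000, Clinpro "Tooth Crème, or MI-Paste Plus has an effect on the formation and resolution of white spot lesions". It names no comparator.

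**Allocation.** Section 13 adds: "This study will include 90 patients in the UAB Orthodontic Clinic". Section 15d divides them: "Three groups of 30 subjects (one group with Clinpro™ 5000, one group with MI-Paste Plus, and one group with Clinpro™ Tooth Crème". Patients are assigned by slips drawn from an envelope, "on which 30 of each study product (i.e., Clinpro™ 5000, MI-Paste Plus, or Clinpro™ Tooth Crème) will be written".

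**Traces of a control.** The blinding text in section 15d states: "Subjects and study administrator will not know if the investigational paste or placebo is being administered". SAP item (1) contrasts a control with the study groups on EDI scores. Neither document says who the control is, and no patient is allocated to a placebo.

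**Measurement.** The section 16e table lists a caries risk assessment once at the start and an evaluation for reduction of lesions once at the end of treatment. It lists no lesion or EDI score at baseline. Under section 16a every patient uses a non-fluoridated toothpaste during the washout, so that toothpaste is not a parallel arm.

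**Analysis.** Beyond item (1), the SAP says only that standard methods were used. It gives no significance level, power, effect size or rule for interpretation.

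**The concern.** Whether a product has an effect is a question about what would have happened without it. The trial has no concurrent group that shows this. It can rank the products against each other but cannot place any of them relative to no product or to ordinary toothpaste.

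What is at stake is how the result will be read. A non-significant comparison could be reported as evidence that no product works, and an improvement within an arm as evidence that the product works. The design supports neither conclusion, and nothing in the SAP rules them out. The stray references to a placebo and a control add to the risk, because a reader may believe that an absolute comparison was made.

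**Working it through.** **1. Is anyone left for a control?** The plan's total is 90. The arms give 30 + 30 + 30 = 90, so the stated total is reproduced and 90 − 90 = 0 patients remain. The envelope agrees: 30 slips for each of three products and none for anything else.

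**2. What can the between-arm test see?** The documents give no alpha, SD or effect size, so these inputs are assumptions: one-way ANOVA, n = 30 per arm, alpha = 0.05, and δ = each product's effect in SD units relative to an untreated arm that does not exist in this trial. The rejection probability depends on δ only through

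λ = 30 × Σ(δᵢ − mean δ)², referred to a noncentral F with 2 and 87 df.

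| Assumed effects (SD) | Meaning | Σ(δᵢ − mean δ)² | λ | Rejection |
|---|---|---|---|---|
| 0, 0, 0 | none works | 0 | 0 | 5.0% |
| 0.5, 0.5, 0.5 | all work equally | 0 | 0 | 5.0% |
| 1, 1, 1 | all work equally | 0 | 0 | 5.0% |
| 2, 2, 2 | all work equally | 0 | 0 | 5.0% |
| 1.0, 0.75, 0.5 | all work, unequally | 0.125 | 3.75 | 38% |
| 1.0, 0.5, 0.5 | all work, one better | 0.1667 | 5.0 | 49% |
| 0.5, 0, 0 | only one works | 0.1667 | 5.0 | 49% |
| 1.3, 0.5, 0.5 | all work, one much better | 0.4267 | 12.8 | 89% |

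The first four rows show that equal efficacy of any size looks the same as no efficacy. The fifth, sixth and eighth rows show that unequal efficacy can be detected. The sixth and seventh rows have identical differences between arms, hence the same λ and the same 49%. In one the two poorer products work, and in the other they do not. Adding a constant to every δ leaves λ unchanged, so the comparison carries no information about that constant.

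**3. How large must a difference be?** For 80% power on one pair with 30 per arm, the detectable difference is (1.960 + 0.842) × √(2/30) = 0.72 SD. With Bonferroni over three pairs it is (2.394 + 0.842) × √(2/30) = 0.84 SD. Products that work to similar degrees would therefore usually yield no significant difference, which is the result most open to misreading.

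**4. Could change from baseline supply the absolute effect?** No baseline lesion score is listed in section 16e. Even with one, the change would mix the product with two other influences:
- The appliances. Section 15d starts the products at the beginning of orthodontic treatment, and section 14 says lesions can be detectable within about a month of appliance placement.
- The end of the non-fluoride washout. Any fluoride toothpaste would also end it.

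**5. Does the placebo or control wording supply a comparator?** No. Neither matches an arm. Calling one of the three products the control would make SAP item (1) runnable, but the contrast would still be one study product against another.

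**The case against.** The strongest reply is that the comparative aim is already stated. The study title, in both the protocol and the SAP, begins with the word Comparison, and SAP item (1) is a between-group difference. Section 13 of the form asks for one short lay paragraph, so the sentence may simply be loose wording. This softens the mismatch but does not remove it. Section 13 is where the purpose is stated, and the SAP puts no limit on the conclusions.

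Three stronger readings are tempting, and the documents do not support them.

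- *The trial gives the same result whether all products work or none does.* This holds only for the between-arm test, and only if the products work equally well. Unequal efficacy is detectable, as the 38% to 89% in the table shows. The overall lesion level would differ too, although without a control that difference cannot be attributed to the products.
- *No analysis can say anything about the Purpose.* This goes too far. A real difference between randomised arms implies that at least one product changes the outcome. It does not show which one, or in which direction relative to no product.
- *A control arm was intended and left out.* The documents mention a placebo and a control but do not settle what was meant. The authors must say.

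It is also fair to object that neither document announces a plan to report a null result as no effect. That is true. The risk comes from an absolute Purpose combined with a SAP that is silent on interpretation.

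**Conclusion.** The point holds. Section 13 poses an absolute question for each product, and the design as documented can answer only a relative one, because 0 of the 90 patients are in a group that could show what happens without the products. If the products work equally well, the between-arm test cannot separate all working from none working. If they differ, it still does not show whether the poorer one works. The title narrows the gap without closing it.

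The conclusion rests on the allocation in section 15d and the procedures table in section 16e. It does not depend on the assumed alpha or effect sizes, which serve only as illustration. The 5.0% is simply that assumed alpha.

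A reader might also be drawn to the Background figures ("Approximately, 50 percent of orthodontically treated patients develop white spot lesions in one or more teeth, compared with only 24 percent") as rates without and with a working product. They cannot serve that purpose. The 24 percent refers to people not having orthodontic treatment, the 50 percent is not stated as a four-month rate, and the planned outcome is an EDI score rather than the presence of lesions. Feeding both into a three-arm chi-square test with 30 per arm gives 4.9% rejection with all arms at 24% and 4.8% with all at 50%. Again this is only the assumed 5% alpha, and it is no extra evidence.

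**What to change.** 1. **Protocol section 13.** Restate the Purpose, in line with the study title: to compare Clinpro 5000, Clinpro Tooth Crème and MI-Paste Plus with each other for the formation and resolution of lesions during orthodontic treatment.
2. **Protocol section 15d and SAP item (1).** Reconcile the placebo and control wording with the three arms. Either remove it or name which of the three products is the active reference.
3. **SAP.** Add text such as: Between-product differences in EDI will be reported with 95% confidence intervals. Neither a non-significant difference nor a within-arm change will be reported as showing that a product has, or lacks, an effect relative to no product or ordinary toothpaste.

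The cost is a few sentences. Arms, enrolment and procedures stay as they are, and the sponsor gives up only an absolute-effect claim that the design cannot support. Keeping the absolute question would instead require a defined and allocated concurrent control, which is a redesign and not an edit.

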This proprietary formula successfully integrates these components, enhancing, rather than compromising, the product's performance. During the manufacturing process, a protective barrier is created around the calcium allowing it to coexist with the fluoride ions. Think of this as a bubble that transports the Tri-Calcium Phosphate to the teeth. As the toothpaste comes in contact with saliva during brushing, the barrier breaks down and makes the calcium, phosphate and fluoride readily available to the tooth. The tooth naturally absorbs these components, helping to prevent the initiation and further progression of demineralization and allowing remineralization to occur.

15. Participants (Screening and Selection)

- a.** How many participants are to be enrolled at UAB? 90

If multi-center study, total number at all centers: _____

- b.** Describe the characteristics of anticipated or planned participants.

Sex: both males and females

Race/Ethnicity: all races

Age: patients age 12-60 with adult dentition, i.e., permanent teeth (including adolescents)

Health status: medically fit and well

Note. If data from prior studies indicate differences between the genders or among racial/ethnic groups in the proposed research or if there are no data to support or to negate such differences, Phase 3 clinical trials will be required to include sufficient and appropriate entry of gender and racial/ethnic subgroups so that trends detected in the affected subgroups can be analyzed. If ethnic, racial, and gender estimates are not

included in the protocol, a clear rationale must be provided for exclusion of this information. If prior evidence indicates that the results will not show gender or racial differences, researchers are not required to use gender or race/ethnicity as selection criteria for study participants. They are, however, encouraged to include these groups. See Section II. Policy of the [NIH POLICY AND GUIDELINES ON THE INCLUSION OF WOMEN AND MINORITIES AS SUBJECTS IN CLINICAL RESEARCH – Amended, October, 2001](#)) for further details.

c. From what population(s) will the participants be derived?

patients coming to clinic for orthodontic treatment

Describe your ability to obtain access to the proposed population that will allow recruitment of the necessary number of participants:

orthodontic clinic

Describe the inclusion/exclusion criteria:

INCLUSION CRITERIA

1. Permanent dentition

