- We will require all patients a two weeks washout period, during which time we will give them very specific brushing instructions for using a non-fluoridated product such as Tom's of Maine toothpaste. These are the same instructions that we will require them to follow with whichever product that the patient will later be randomized to use in the trial, i.e. Clinpro™ 5000, Clinpro™ Tooth Crème, or MI-Paste Plus. This will ensure that all patients will use the same application technique, even though not all patients would be of the same level of potential decay. This washout period will last the same length of time for all patients, even though it will not begin simultaneously for all patients.
- Patient will brush on randomized product for two minutes twice daily for 4 months. After brushing on the product, patients should not rinse their mouths with water. Rather, they should just expectorate (spit). Patient should also not eat or drink for 30 minutes following the treatment. No other inconvenience, danger, or discomfort is expected as a result of study methodology.
- b. What is the probable length of time required for the entire study (i.e., recruitment through data analysis to study closure)?

16 weeks

- c.** What is the total amount of time each participant will be involved?
Subjects will be reviewed every 4 weeks. Subjects will be reviewed on four weekly intervals.
- d.** If different phases are involved, what is the duration of each phase in which the participants will be involved? If no phases are involved, enter "not applicable."
not applicable

- e. List the procedures, the length of time each will take, and the frequency of repetition, and indicate whether each is done solely for research or would already be performed for treatment or diagnostic purposes (routine care) for the population. *Insert additional table rows as needed.*

Procedure	Length of Time Required of Participants	Frequency of Repetition	Research (Res) -OR- Routine Care
A caries risk assessment will be used to determine the caries risk of all patients enrolled into the study.	~10 minutes	once, at start of treatment	 Res  Routine
Patient brushes on study paste at home.	2 minutes	twice daily	 Res  Routine
Patients will be reviewed every 4 weeks		twice, every 4 weeks	 Res  Routine

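### The blinding statement describes a placebo the trial does not have, and the plan names neither a way of masking the products nor a blinded EDI scorer

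*Protocol*

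**What the plan says.** Protocol item 15d sets out the groups as "Three groups of 30 subjects (one group with Clinpro™ 5000, one group with MI-Paste Plus, and one group with Clinpro™ Tooth Crème) each". Item 15a gives the total: "How many participants are to be enrolled at UAB? 90". Items 13 and 16a list the same three products.

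On blinding, item 15d says "Subjects and study administrator will not know if the investigational paste or placebo is being administered" and continues "However, the PIs will know". On allocation, it has the PIs "drawing individual slips of paper from an envelope on which 30 of each study product" is written. On dispensing, it says "Each subject will receive product based upon the treatment type written on the paper selected by PIs".

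On outcome assessment, the table in item 16e lists one evaluation of white spot lesions at the end of treatment, marked as routine care, and names no assessor. The SAP (Results and Statistics) compares a control with the study groups on EDI scores. It does not say which arm is the control and does not mention blinding. Its section on data collection says only that people from the sponsor, or acting for it, collected and analysed the data. SAP Figure 1 describes the EDI as a score from 0 to 3 for each of four areas on the facial surface of each tooth, according to how much of the area is decalcified.

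**The concern.** The blinding sentence is written for a comparison of one paste with placebo, whereas this trial compares three named products. A sentence that does not fit the design cannot tell a reader who is blind to what.

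The procedure around it does not fill the gap. The people who draw the slips know the product, each slip carries a product name, and the subject is given the product on the slip to use at home twice daily for 4 months. No step between slip and subject is described that would hide the product's identity.

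The comparison rests on EDI, which is an examiner's visual judgement of area. An examiner who knows the product can score one arm more leniently than another without intending to. A subject who knows the product may brush differently or answer the satisfaction questionnaire (item 16e) differently. The trial could also be reported as blinded on the strength of a sentence that does not describe it.

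**Working it through.** **Step 1: is there room for a placebo group?**
- Groups (item 15d): 3 products × 30 subjects = 90.
- Enrolment (item 15a): 90.
- Slips (item 15d): 3 products × 30 = 90, all for named products.
- Left for a placebo group: 90 − 90 = 0.

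The plan's total of 90 is reproduced exactly by the three product groups. The only other paste in the protocol is the non-fluoridated one in item 16a, introduced with "We will require all patients a two weeks washout period". It is given to everyone before randomization, so it is not a comparison arm and cannot be the placebo in item 15d.

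**Step 2: who is stated to be blind, and by what means?**
- Subjects: stated to be blind. No means is given in item 15d, in item 16 or in the SAP.
- Study administrator: stated to be blind. The role appears only in item 15d, and its duties are not described.
- PIs: stated to know.
- EDI scorer: not identified in item 16e. The SAP says only that the sponsor's side collected data, which neither names a scorer nor says what the scorer knows.

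Nothing in these passages bars a PI, or anyone else who knows the product, from scoring EDI.

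**Step 3: what could a biased scorer do?** The documents give no SD, no test and no estimate of bias, so this is an illustration under stated assumptions: two arms, all 30 per arm analysed, a two-sided 5% z-test, no true difference, and a net difference in bias of *b* SD between the two arms.
- Standard error of the difference = √(2/30) = 0.258 SD.
- Under the bias, Z has mean *b*/0.258 and variance 1. The false-positive rate is the chance that Z falls outside ±1.96.

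| Net bias *b* between arms (SD, assumed) | Mean of Z | False-positive rate |
|---|---|---|
| 0.1 | 0.39 | 6.7% |
| 0.2 | 0.77 | 12.1% |
| 0.3 | 1.16 | 21.3% |

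Only the difference in bias between arms counts. A shift common to both arms cancels.

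**The case against.** A reader might infer that subjects are handed branded tubes and so know what they are using, and that blinding has therefore failed. The documents do not support this. They never describe the packaging, and the protocol says that subjects will not know. The remark in item 14, "They are available exclusively from 3M ESPE", concerns commercial supply of the two Clinpro products. It says nothing about trial packs or about MI-Paste Plus.

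A reader might also infer that the PIs score the EDI. That is possible under the plan but not stated, and the SAP's sentence on data collection points to the sponsor's side.

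Silence is also weaker evidence here than in a full trial protocol. This is an ethics-board form, and item 15d asks for groups and numbers, not for masking. Item 7 calls for a Drug Review Sheet if drugs are used, and item 3 refers to an attached Clinical Trial Agreement. Neither is available, and some front pages were removed. A packaging step could be described in any of them.

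Finally, the false-positive rates are not evidence about this trial. With three products and no placebo, the documents give no basis for the direction or size of a bias between arms, and the SAP names no test.

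All of this stands, and it limits the point. It does not rescue the placebo wording, which is contradicted within item 15d itself. Nor does it supply a blinded scorer, since the SAP sentence does not say what the data collectors knew.

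**Conclusion.** The contradiction is certain: the blinding statement refers to a placebo, and all 90 subjects and all 90 slips belong to three named products. It is also clear that the available text describes no masking of the products and no blinded EDI scorer, while the PIs know the allocation. Scoring of the main outcome by someone who knows the product is therefore left open.

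It is not established that subjects learn their product, that the PIs score, or that any bias occurred. The conclusion on masking and scoring rests on the two documents as available, and an attachment could change it. The rates of about 7%, 12% and 21% show only how sensitive a two-arm test with 30 per arm would be to an assumed net bias of 0.1, 0.2 or 0.3 SD. They do not estimate the bias in this trial. The point should be corrected because it bears on the credibility of the EDI comparison and on how the trial may be described.

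**What to change.** 1. Rewrite the blinding sentence in item 15d for the three products, and say for each role who is blind to what.
2. Require the EDI to be scored by existing personnel, at the site or acting for the sponsor, who are competent in the index and have no access to the slips or the products. Bar the PIs from scoring. The study administrator should not be assigned this task by default, because the documents show no competence in EDI for that role.
3. Either state how the tubes are coded and who dispenses them, or drop the claim that subjects are blind and report the trial as assessor-blind only. That label holds only if the scorer in step 2 is in place and subjects are asked not to reveal their product at assessment.
4. If scoring has already been done, as the SAP's partly past tense may suggest, report who scored, what they knew and how the products were packed, and claim no more blinding than that supports.

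The cost is a wording change and minor logistics to keep the scorer apart from slips and products. Coded labels for 90 subjects are an added cost only if the subject-blind claim is kept. Dropping it weakens the blinding claim. No arm or sample size changes.

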 - Fetuses: Attach [SPRF—Pregnant Women, Fetuses, Neonates/Nonviable Neonates](#)
 - Neonates/Nonviable Neonates: [SPRF—Pregnant Women, Fetuses, Neonates/Nonviable Neonates](#)
 - Prisoners: Attach [SPRF—Prisoners](#)
 - Minors (<19 years old): Attach [SPRF—Minors](#)
 - Employees or students at institution where research conducted
 - Persons who are temporarily decisionally impaired
 - Persons who are permanently decisionally impaired (e.g., mentally retarded)
 - Non-English Speakers

For each box checked, describe why the group is included **and** the additional protections provided to protect the rights and welfare of these participants who are vulnerable to coercion: _____

- f. List any persons other than those directly involved in the study who will be at risk. If none, enter "None": None
- g. Describe the process (e.g., recruitment, chart review) that will be used to seek potential participants (e.g., individuals, records, specimens). Research recruitment by non-treating physicians/staff may require completion of Partial Waiver of Authorization for Recruitment/Screening. (See <http://main.uab.edu/show.asp?durki=61981>.)
All orthodontic patients who meet the inclusion criteria will be invited to participate.
- h. If you will use recruitment materials (e.g., advertisements, flyers, letters) to reach potential participants, attach a copy of each item. If not, identify the source (e.g., databases) from which you will recruit participants.
No, clinic patients only.
- i. Describe the procedures for screening potential participants.
All orthodontic patients who meet the inclusion criteria will be invited to participate.

16. Protocol Procedures, Methods, and Duration of the Study—in nontechnical language

- a. Describe the study methodology that will affect the participants—particularly in regard to any inconvenience, danger, or discomfort.

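### Unblinded PIs draw loose slips from one shared envelope, with no recorded enrolment lock, draw log or final-slip rule: concealment is weak, the likely bias from isolated lapses is small, and a better method costs little

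*Protocol*

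**What the plan says.** **Allocation (Protocol 15d).** Two named people "will randomly choose subjects by drawing individual slips of paper from an envelope on which 30 of each study product" is written. Then: "Each subject will receive product based upon the treatment type written on the paper selected by PIs". Subjects and the study administrator are to be blind. The next sentence is "However, the PIs will know".

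**Eligibility (15c).** Two criteria rest on judgement. Inclusion criterion 2 is "Patients that in the opinion of the investigator will be compliant with the use of the paste". Exclusion criterion 1 is "Any medical or dental condition that in the opinion of the investigator could impact study results during the expected length of the study".

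**Order of events.** Item 15i: "All orthodontic patients who meet the inclusion criteria will be invited to participate". Item 16a describes the washout and refers to "whichever product that the patient will later be randomized to use in the trial". It adds that washouts do not all start at the same time.

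**Baseline and consent.** Item 16e: "A caries risk assessment will be used to determine the caries risk of all patients enrolled into the study". This is done once at the start of treatment, with no stated order relative to the draw. Item 20d allows the PI or the Research Coordinator to conduct the consent interview.

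**Analysis.** The SAP, under Results and Statistics, refers only to standard methods. It names no analysis population and does not say that participants are analysed in the group they were allocated to.

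**The concern.** Randomisation protects the comparison only if nobody can let knowledge of the next or current assignment affect who enters, or who stays in, each arm. Here the slips are loose in one envelope, the people drawing them know the product, and a PI may also be the person taking consent. Entry is staggered, so the draws are probably made one at a time. Three things are not written down:

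- that consent and eligibility are recorded as final before a slip is read;
- that each draw is logged;
- that a drawn slip cannot be returned, swapped or followed by an opinion-based exclusion.

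Two things are at stake. The first is selection bias, which cannot be adjusted away if it acts on a trait nobody measured. The second is auditability: without a dated record, a properly made draw cannot be told apart from an improper one.

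**Working it through.** **The plan's own figure.** Three products × 30 slips = 90, which matches the enrolment in item 15a. The documents give no alpha, power, effect size or SD, so the size of a bias cannot be calculated from them. What follows is an illustration.

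**Assumptions (not from the documents).** Two arms of 30 are compared by a two-sided 5% t-test with no true difference. Half of the patients have the better prognosis, and D, the gap between better and worse, is 0.5 to 1.0 SD. SE = √(2/30) = 0.258 SD. False-positive rates come from the noncentral t with 58 df.

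**Route 1: exclusion after the draw.** Each of k poor-prognosis patients in one arm is replaced by an average patient, so the shift is k × (D/2)/30 = kD/60.

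**Route 2: redraw.** A poor-prognosis patient draws favoured arm A, the slip goes back, and one new slip is drawn. With probability about 2/3 an average patient later takes that place in A. With probability about 1/3 the poor patient lands in comparator B in place of an average one. The A–B shift is (2/3 + 1/3) × (D/2)/30 = D/60 per redraw, the same as route 1.

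| Events, routes 1 and 2 | D = 0.5: shift (SD), rate | D = 1.0: shift (SD), rate |
|---|---|---|
| 1 | 0.008, 5.0% | 0.017, 5.0% |
| 3 | 0.025, 5.1% | 0.050, 5.4% |
| 5 | 0.042, 5.3% | 0.083, 6.2% |

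A direct simulation of five redraws from 30/30/30 slips (20,000 trials per case) gave 5.4% and 6.3%.

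**Route 3: exchange.** Swapping m good-for-poor pairs between the two arms changes both means, so the shift is 2mD/30, four times as much per event.

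| Pairs exchanged | D = 0.5: shift (SD), rate | D = 1.0: shift (SD), rate |
|---|---|---|
| 1 | 0.033, 5.2% | 0.067, 5.7% |
| 2 | 0.067, 5.7% | 0.133, 8.0% |
| 3 | 0.100, 6.7% | 0.200, 11.9% |
| 5 | 0.167, 9.7% | 0.333, 24.6% |

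**If the trait is measured.** Simulated exchange of three or five pairs, followed by adjustment for the trait, gave rates of 4.7% to 5.4%. A baseline chi-square test on the trait was significant in about 8%, 35% and 74% of trials with 1, 3 and 5 pairs. Caries risk is assessed in everyone enrolled, so steering on it could be seen in part and adjusted for. Steering on an unmeasured trait could not.

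**Predictability of fixed totals.** Someone who tracked the remaining slips and always guessed the commonest would be right for about 36.8 of 90 assignments (41%, against 33% by chance) and for about 60% of the last ten. On average the last 1.5 assignments are fully determined. This follows from the exact 30/30/30 totals, assuming draws without replacement, and is not specific to loose slips.

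**The case against.** The strongest reply is that this is real randomisation with a sensible order. Eligible patients are invited, complete the washout and are then randomised, and the product is the one on the slip drawn. Returning a slip would already depart from the procedure, so the complaint is that the plan does not also forbid departures from itself. This stands in part. It answers any claim that the method is invalid, but an implied order is not a recorded lock, and it leaves nothing to check afterwards.

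The second reply is that the large figures belong to exchange alone. Exchange needs two assignments open at once, although entry is staggered, and amounts to deliberate tampering, which a log deters only partly. That stands. Redraws and exclusions should be judged on their own, small, figures.

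Third, expected compliance is an obvious unmeasured trait, yet inclusion criterion 2 admits only patients already judged likely to comply. That also stands in part: an even split with a gap of 0.5 to 1.0 SD is generous for that trait.

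A reader might infer that one unblinded person judges eligibility, takes consent and draws the slip, or that the PIs choose the product. The documents support neither. They permit overlap of roles but do not state it, and title and staffing pages were removed before review, so silence on the division of duties should not count against the plan. Item 15d describes a draw, not a choice, and nothing suggests that slips were returned or patients excluded selectively.

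**Conclusion.** The point holds as a gap in safeguards, not as a flaw that invalidates the allocation. The draw is made by people who know the product, from one shared envelope, and no readable text fixes enrolment beforehand, records the draw or makes it final. Concealment is weak and correctness could not be demonstrated.

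The size of any bias cannot be derived from the documents. On the assumptions above, up to five redraws or post-draw exclusions leave the false-positive rate at no more than about 6 to 7%, and one or two events hardly matter. Rates of about 7 to 12% (three pairs) or 10 to 25% (five pairs) need deliberate exchange on an unmeasured trait and should not be quoted as the effect of ordinary lapses. The gap D, the even split and the event counts are all assumed.

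This is a cheap improvement worth making, because steering on an unmeasured trait cannot be repaired at analysis.

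**What to change.** In Protocol 15d, keep 30/30/30 but replace the slips with a pre-generated random order in sequentially numbered, opaque, sealed envelopes or product kits numbered 1 to 90. Existing staff who neither enrol patients nor judge eligibility should prepare and hold them. This must not be the PIs, because someone who prepares the sequence knows it in advance, which a blind draw avoids.

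Open the next envelope only after consent, eligibility and the baseline caries risk assessment are recorded, and after the participant ID and date are written on it. Keep a dated allocation log and allow no reopening or reassignment.

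Envelopes do not prevent exclusions after allocation. Add to the SAP that every randomised participant is analysed in the allocated group, whether or not the product is later stopped.

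The cost is ninety envelopes or labels, a log, two or three sentences in 15d and one in the SAP. There are no extra patients, visits or measurements, and the downside is minor preparation time. The change does not remove predictability near the end of a fixed 30/30/30 list, or later bias from PIs who know the treatment.
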